21 CCI

21.1 CCI

CCI

- [Redacted]
 - [Redacted]
 - [Redacted]
- [Redacted]
- [Redacted]
 - [Redacted]
 - [Redacted]

21.2 CCI [REDACTED]

CCI [REDACTED]

[REDACTED]

[REDACTED]

21.3 CCI [REDACTED]

CCI [REDACTED]

21.4 CCI [REDACTED]

CCI [REDACTED]

[REDACTED]

[REDACTED]

[REDACTED]

21.5 CCI [REDACTED]

CCI [REDACTED]

[REDACTED]

CCI [Redacted]

21.6 CCI [Redacted]

CCI [Redacted]

- I [Redacted]
- I [Redacted]
- I [Redacted]
- I [Redacted]
- I [Redacted]
- I [Redacted]
- I [Redacted]
- I [Redacted]
- I [Redacted]

[Redacted]

- I [Redacted]

[Redacted]

- I [Redacted]
- I [Redacted]
- I [Redacted]
- I [Redacted]
- I [Redacted]
- I [Redacted]

- CCI [REDACTED]

[REDACTED]

[REDACTED]

- [REDACTED]
- [REDACTED]

[REDACTED]	[REDACTED]	[REDACTED]

CCI [Redacted]	[Redacted]	[Redacted]
[Redacted]	[Redacted]	[Redacted]

22 Details on Data Handling

22.1 Derived Variables

22.1.1 eDiary

22.1.1.1 Determination of Migraine Days and Headache Days

Headache day:

- A day is considered a headache day if a headache (as identified through a unique headache ID) has been reported to take place on that day with a duration of at least 30 minutes on that day, or if the day is a migraine day.
- A day is considered a non-headache day if one or more headaches (as identified through a unique headache ID) have been reported to take place on that day, but none

of them make the day qualify as a headache day as defined above. Or no headaches have been reported to take place on that day, but the headache diary was completed on that day, confirming that the participant did not have a headache to report.

- A day is considered a missing observation for headache day, if it is not a headache day or a non-headache day, as defined above.

Migraine day:

- A day is considered a migraine day if a headache (as identified through a unique headache ID) has been reported to take place on that day and fulfils the criteria for a migraine on that day (based on the criteria specified in section 4.6.2).
- A day is considered a non-migraine day if one or more headaches (as identified through a unique headache ID) have been reported to take place on that day and headache characteristics have been reported for all headaches on that day, but none of them make the day qualify as a migraine day as defined above. Or no headaches have been reported to take place on that day, but the headache diary was completed on that day, confirming that the participant did not have a headache to report.
- A day is considered a missing observation for migraine day, if information (e.g. headache characteristics) is missing in the headache diary to be able to classify the day as a migraine day or a non-migraine day.

If characteristics/symptoms for the same headache (identical headache ID) are reported more than once within the same day, then that day is considered a migraine day, if at least one set of characteristics make the day qualify as such.

22.1.1.2 Monthly Migraine Days, CCI

The following describes the derivation of MMDs.

CCI

For a given headache, determine whether it is a migraine attack as defined in section 4.6.4. If that is the case, then each day of the headache with a headache duration of at least 30 minutes or where the day itself fulfils the Migraine Day definition in section 4.6.2 is considered a migraine day according to Derivation method 1.

CCI

[Redacted]

[Redacted]

[Redacted]

22.1.1.3 Migraine/CCI Response Variables

The following describes the derivation for response for monthly migraine/CCI days.

The following response variables will be derived: 50%, CCI. A responder is defined as a participant who achieves a $\geq 50\%$, CCI reduction in MMDs/CCI respectively, compared to the baseline MMDs/CCI. The derivation of these response endpoints will be based on the MMD/CCI.

For each 4-week interval after IMP dosing, the response status of a participant will be derived based on the percentage change from baseline in MMDs/CCI. If the MMDs/CCI value is missing for the 4-week interval in question, the response status will also be missing.

22.1.1.4 CCI

[Redacted]

22.1.1.5 CCI

[Redacted]

22.1.1.6 CCI

[Redacted]

- CCI [REDACTED]

[REDACTED]

[REDACTED]

[REDACTED]

[REDACTED]

22.1.1.7 CCI [REDACTED]

- [REDACTED]
- [REDACTED]

[REDACTED]

[REDACTED]

22.1.1.8 CCI [REDACTED]

- [REDACTED]
- [REDACTED]
- [REDACTED]

- CCI [REDACTED]

[REDACTED]

[REDACTED]

[REDACTED]

[REDACTED]

[REDACTED]

22.1.2 CCI [REDACTED]

22.1.2.1 CCI [REDACTED]

[REDACTED]

22.1.2.2 CCI [REDACTED]

[REDACTED]

[REDACTED]

22.1.2.3 CCI [REDACTED]

[REDACTED]

CCI [Redacted]

22.1.2.4 CCI [Redacted]

CCI [Redacted]

[Redacted]

[Redacted]

[Redacted]

CCI [Redacted]

[Redacted]

[Redacted]

[Redacted]

[Redacted]

[Redacted]

[Redacted]

[Redacted]

- [Redacted]
- [Redacted]
- [Redacted]

[Redacted]

[Redacted]

22.1.2.9 **CCI**

[REDACTED]

[REDACTED]

22.1.3 Handling of Data After ICE “Use of Preventive Therapy”

In the case of the intercurrent event “use of preventive therapy” occurs (see section 12.3.2), the data collected after preventive medication intake will be disregarded and set to missing.

22.2 Assigning Data to Visits

See section 4.1 for definition of Baseline values.

22.2.1 Safety Variables

Laboratory Tests, Vital Signs, Body Weight, ECG and C-SSRS

Assessments at unscheduled visits and withdrawal visits will be assigned to a nominal visit, according to the visit windowing specified in Panel 6. Assessments for participants not receiving an infusion of IMP will be assigned to Visit 2 (Baseline).

Panel 6 Visit Windows - Laboratory Tests, Vital Signs, Body Weight, ECG and C-SSRS

Nominal Visit Number	Nominal Visit Week	Nominal Visit Day	Time Window
V1 (Screening Visit)	-4	-28	Day -28 and before IMP infusion
V2 (Baseline Visit)	0	0	Same day as IMP infusion (Day 0) and prior to IMP infusion on that date
V3	2	14	After start of IMP infusion to Day 21
V4	4	28	Day 22 to Day 41 after start of IMP infusion

Nominal Visit Number	Nominal Visit Week	Nominal Visit Day	Time Window
V5	8	56	Day 42 to Day 69 after start of IMP infusion
V6	12	84	Day 70 to Day 98 after start of IMP infusion

If there is more than one assessment at a visit (either due to multiple assessments or because an unscheduled or withdrawal visit assessment is mapped to a nominal visit with an already existing value) the value that will be used in summary tables by visit will be the one closest to the nominal day for the visit but prioritizing values from scheduled visits above values from withdrawal or unscheduled visits. In the ordering of multiple values, assessments without recorded time will come after assessments with recorded time and the first in the ordering will be selected.

22.3 Handling Missing or Incomplete Dates/Times

22.3.1 Missing Headache End Date and Time

If the end date and time for a headache recorded in the eDiary is missing, the headache end date and time will be imputed with the end of trial date.

Note that for each participant, it is only possible to have a missing end date and time for the last headache entered, since a participant needs to complete a headache entry in order to report a new headache in the headache eDiary.

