8.11 End-of-study Definition

The end of the study for an individual patient is defined as the last protocol-specified contact with that patient. The overall end of the study is defined as the last protocol-specified contact with the last patient ongoing in the study.

9 Assessments

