4.6.2 Migraine Day

A migraine day is defined as a day with a headache that meets following criteria listed below:

1. A headache that:

Lasted 4 hours or more and had at least 2 of the following:

1. Unilateral location
2. Pulsating quality
3. Moderate or severe pain intensity
4. Aggravation by or causing avoidance of routine physical activity

and had at least 1 of the following:

1. Nausea and/or vomiting
 2. Photophobia and phonophobia
2. Or A headache that lasted 30 minutes or more and the participant had an aura with the headache (migraine with aura*)
3. Or A headache that lasted 30 minutes or more and meets 2 of the 3 following criteria (probable migraine**):
- Lasted 4 hours or more
 - Had at least 2 of the following:
 1. Unilateral location
 2. Pulsating quality
 3. Moderate or severe pain intensity
 4. Aggravation by or causing avoidance of routine physical activity
 - Had at least 1 of the following:
 1. Nausea and/ or vomiting
 2. Photophobia and phonophobia
4. Or a day with a headache that is successfully treated with a triptan, ergotamine, or other migraine-specific acute medication CCI

If a headache lasts ≥ 72 hours, the days will still be counted as *headache days* or *migraine days* as aligned with the IHS guidelines.

A day where the symptoms are not recorded for an ongoing headache (missed data entry) will be classified as a headache day.

Further details on the definitions:

CCI

CCI [Redacted]

CCI [Redacted]

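### An open last headache is run to the end of trial with no visible cap at the last diary entry, so unobserved days in Weeks 1-4 can count as headache days in the secondary endpoint MHDs

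*SAP*

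**What the plan says.** SAP 22.3.1 deals with a headache that has no recorded end: "the headache end date and time will be imputed with the end of trial date". It adds that "it is only possible to have a missing end date and time for the last headache entered", because a headache must be closed before a new one can be opened.

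Three other rules decide what happens to the days inside that imputed span:

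- SAP 4.6.2 (Protocol 9.1.3 carries the same sentence): "A day where the symptoms are not recorded for an ongoing headache (missed data entry) will be classified as a headache day".
- SAP 22.1.1.1: a day is a headache day if a headache "has been reported to take place on that day with a duration of at least 30 minutes on that day", or if it is a migraine day.
- SAP 22.1.1.1 again: "A day is considered a missing observation for headache day, if it is not a headache day or a non-headache day, as defined above".

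The visible SAP does not define the end of trial date. Protocol 8.11 gives a patient-level end ("The end of the study for an individual patient is defined as the last protocol-specified contact with that patient") and a second, study-wide end tied to the last ongoing patient.

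Change in MHDs over Weeks 1-4 is a secondary endpoint. SAP 12.4 analyses it by ANCOVA on the FAS, and SAP 12.2 places it outside type 1 error control.

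**The concern.** Only the last headache can be open, so during Weeks 1-4 the rule comes into play where diary entries stopped in the middle of a headache. If that participant stays in the trial, the imputed end lies after Day 28. Each later day then falls within an ongoing headache, has more than 30 minutes of imputed headache, and has no symptom entry. Section 4.6.2 calls such a day a headache day, and under 22.1.1.1 a headache day is not missing.

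Unobserved days would then enter the MHD count at the worst possible value. Elsewhere the plan handles unobserved diary data differently: Protocol 16.8.2 prorates when 14 or more of 28 days are recorded (a rule worded for migraine days), and SAP 12.3.3 uses multiple imputation for missing monthly migraine days (MMDs). No reason for a different treatment here is visible. Two programmers could also derive different MHD values from the same diary, depending on which sentence they take to govern.

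**Working it through.** The plan gives no figure of its own on this point, so there is none to reproduce. The check has two parts.

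**Reading the rules together.** Take a participant with entries up to Day *s*, a headache open on Day *s*, no later entries, and trial contact beyond Day 28.

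1. 22.3.1 sets the headache end after Day 28.
2. Days *s*+1 to 28 are then days of an ongoing headache with no symptoms recorded, which 4.6.2 classes as headache days.
3. Under 22.1.1.1 they are therefore not missing for headache.
4. If instead the reporting condition in 22.1.1.1 is read strictly, nothing was reported on those days and they are missing. Sections 4.6.2 and 22.1.1.1 then conflict, and the visible text does not say which prevails.

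For migraine days the visible rules also diverge. 22.1.1.1 says "A day is considered a missing observation for migraine day, if information (e.g. headache characteristics) is missing in the headache diary", while Derivation method 1 in 22.1.1.2 counts, for a headache that is a migraine attack, "each day of the headache with a headache duration of at least 30 minutes". Redaction hides which takes precedence.

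**Size for MHDs.**

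From the documents: 28-day window; 92 planned per arm (high dose and placebo); SD 5.6, stated for MMDs; eligibility ceiling of 26 headache days.

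Assumed: the 14-day proration rule also applies to MHDs; no gaps before the stop; stop days spread evenly over Days 14-27; headache-day rate *h* before the stop of 40-70%; SD 5.6 also holds for MHDs.

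With *d* headache days recorded by Day *s*:

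- Rule value = *d* + (28 − *s*)
- Prorated value = *d* × 28 / *s*

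| Stop day *s* | *d* | Rule value | Prorated value | Difference |
|---|---|---|---|---|
| 14 | 9 | 9 + 14 = 23 | 18.0 | 5.0 |
| 18 | 11 | 11 + 10 = 21 | 17.1 | 3.9 |
| 21 | 13 | 13 + 7 = 20 | 17.3 | 2.7 |
| 25 | 12 | 12 + 3 = 15 | 13.4 | 1.6 |

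In expectation the difference is (28 − *s*)(1 − *h*). For stops on Days 14 to 27, 28 − *s* runs from 14 down to 1, with mean 7.5:

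- *h* = 0.40: 7.5 × 0.60 = 4.5 days
- *h* = 0.70: 7.5 × 0.30 = 2.25 days
- *h* = 26/28: 7.5 × 2/28 = 0.54 day

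Shift in an arm mean from one affected participant: 4.5/92 = 0.049 day and 2.25/92 = 0.024 day.

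Standard error of the arm difference: 5.6 × √(2/92) = 0.826 day. The shift is therefore 0.024/0.826 = 3.0% to 0.049/0.826 = 5.9% of a standard error.

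**Effect of the undefined date.** For a participant who stays in the trial, both ends in Protocol 8.11 fall after Day 28 and give the same result. They differ only for someone lost early. For a participant last contacted on Day 14, with the diary stopping that day mid-headache and 9 headache days recorded, the patient-level end adds 0 days (prorated value 18) and the study-wide end adds 14 (value 23).

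**The case against.** The strongest reply is that the visible derivation rule already excludes these days. 22.1.1.1 asks for a headache reported on the day itself, and after the diary stops nothing is reported. On that view the missed-entry sentence in 4.6.2 covers only skipped entries inside a headache that was later resumed or closed. This reading is possible but not decisive: 22.3.1 exists to give an open headache a duration, and 4.6.2 expressly covers days without symptom entries.

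The second reply is redaction, and it stands as a limit. SAP 4.6 sends the handling of missing diary data to 22.1.1; the heading and most of the body of 22.1.1.2 are blacked out, as are the further details after the missed-entry sentence in 4.6.2. A rule for MHDs could be hidden there as easily as one for MMDs.

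The third is reach, and it also stands. Sites check diary compliance at visits and continuously (Protocol Panel 2, footnote h), and the diary is closed out at Week 12, or at Week 4 for most patients who withdraw early. The FAS requires a valid MMD value for Weeks 1-4, which would normally remove participants with 13 or fewer recorded days. Nothing in the documents shows that even one participant will be affected. Proration is itself a convention: someone who stops mid-headache may be more likely than average to have headache the next day, so the figures above are differences from proration, not errors against the truth.

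A defence of the rule as a conservative convention is weaker. It is not needed for the Weeks 1-4 count when a headache is open at the Week 12 closeout, and it can distort that count when entries stopped earlier.

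A reader might infer that the undefined date is the main fault. The documents do not support that. The imputation is made per participant, so the patient-level end in Protocol 8.11 is the natural reading, and the 0 versus 14 day contrast needs the less plausible one.

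**Conclusion.** On the visible text, following SAP 22.3.1, 4.6.2 and 22.1.1.1 together can turn unobserved Weeks 1-4 days into headache days in MHDs. A cap at the last diary entry would be a better rule. Under the assumptions listed, the difference from proration averages 2.25 to 4.5 days per affected participant and falls to about 0.5 day at the eligibility ceiling. One participant moves an arm mean by 0.02 to 0.05 day, or 3-6% of a standard error. The number affected is unknown and probably small.

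Two stronger conclusions are tempting and are not supported. One is that the primary endpoint is affected: the visible migraine-day rules point in different directions and the deciding text is redacted, so no such claim is made. The other is that the treatment comparison is biased: equal numbers of affected participants per arm give no bias, and nothing in the documents suggests an imbalance.

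Severity is minor, and confidence is limited by the redactions. This is a cheap improvement.

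**What to change.** - In SAP 22.3.1, end an open headache at the close of the last day with an eDiary entry for that headache. State that later days without an entry are missing and do not count as recorded days.
- In SAP 4.6.2, limit the missed-entry rule to days lying between two entries for the same headache.
- Confirm that the migraine-day derivation in 22.1.1.1 and 22.1.1.2 treats these days in the same way.
- If the present rule is kept as a worst-case sensitivity analysis, define the end of trial date as the patient-level end in Protocol 8.11.

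If redacted text already settles the matter, a cross-reference in 22.3.1 is enough.

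The cost is a few sentences, a small programming change, and a noted departure from the missed-entry wording in Protocol 9.1.3, all before unblinding.

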22.3.2 Withdrawal Date

Missing withdrawal dates will not be imputed and time to withdrawal from treatment will not be calculated for missing withdrawal dates.

22.3.3 Medical Disorder Start and Stop Dates

Incomplete dates will not be imputed. Classification of events into *concurrent medical disorders* or *past disorders* will be based on the reported ongoing status.

22.3.4 Medication Start and Stop Dates

Imputation of incomplete or partially missing dates will be performed in order to document the assigned categories specified in section 9.

The algorithm for imputing the start dates will follow the one used for imputing adverse event start dates, see section 22.3.5.

For imputing stop dates, the following will apply, where UK and UKN indicate unknown or missing day and month, respectively:

- UK-MMM-YYYY: Medication end date is imputed with the last day of the month
- UK-UKN-YYYY: Medication end date is imputed with 31-DEC-YYYY

Medications marked as ongoing are considered concomitant medications.

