Anti-migraine agents	
Allowed with restrictions:
 
 Acute treatment of migraine (prescription or over-the-counter medication recommended by a healthcare professional) is allowed provided the treatments used have been stable for at least 14 days prior to the Screening Visit and expected to be maintained until the Safety Follow-up Visit (Week 12). At the discretion of the Investigator, on a case-by-case basis, changes that might be clinically warranted may be made after the Baseline Visit. Any medications in preventive migraine treatment classes that are prescribed for medical conditions other than migraine prevention are allowed if they have been stable in terms of dose and regimen for at

Drug Class	Details
	
least 12 weeks prior to the Screening Visit and until the Safety Follow-up Visit.
 
Disallowed:
 
 • Do not use preventive migraine treatments <1 week prior to the Screening Visit until the Safety Follow-up Visit (Week 12). • Do not use oral anti-CGRP treatment <4 weeks prior to the Screening Visit and until the Safety Follow-up Visit (Week 12). • Do not use CGRP-directed monoclonal antibodies <24 weeks prior to the Screening Visit until the Safety Follow-up Visit (Week 12). • Do not use botulinum toxin for migraine or any other medical/cosmetic reason in the head and/or neck region <16 weeks prior to the Screening Visit and until the Safety Follow-up Visit (Week 12). • Do not use monoamine oxidase inhibitors, ketamine, methysergide, methylergonovine, or nimesulide <12 weeks prior to the Screening Visit and until the Safety Follow-up Visit (Week 12). • Do not use preventive injectable therapy (e.g., trigger point injections, extracranial nerve blocks, or facet joint injections) <8 weeks prior to the Screening Visit and until the Safety Follow-up Visit (Week 12).
Hormones	
 • Hormonal therapy (e.g., contraceptives, hormone replacement therapy) is allowed provided the dose and regimen have been stable for at least 12 weeks prior to the Screening Visit and expected to be maintained until the Safety Follow-up Visit (Week 12).
Immunosuppressants	
 • Do not use immunosuppressants (e.g., systemic steroids, TNF alpha inhibitors, methotrexate) <12 weeks (or at least 5 times the half-life of the medication) prior to the Screening Visit and until the Safety Follow-up Visit (Week 12).

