A concurrent medical, neurological, or psychiatric disorder is a disorder that is ongoing at the Screening Visit. A past medical, neurological, or psychiatric disorder is a disorder that ended prior to the Screening Visit. Social history will be summarized by treatment group.

Summaries of prior preventive treatment failure medications within 10 years prior to the Screening Visit will be presented by treatment group. The number and percentage of participants with each type of prior treatment failure (lack of efficacy, safety/tolerability, or contraindication) will also be presented by treatment group, as well as the number of prior preventive treatment failures.

9 Recent and Concomitant Medication

Recent and concomitant medication will be coded using the *WHO Drug Dictionary* (WHO-DDE, version March 2022 or later).

Medications will be classified according to the start and stop time and summarized by anatomical therapeutic chemical (ATC) code, generic drug name and treatment group. Handling of missing or incomplete dates is specified in section [22.3.4](#).

The following categories will be used:

- Prior medications: Medications with a stop date before IMP infusion
- Concomitant medication: continued after IMP infusion or started at or after IMP infusion

The tables for prior and concomitant medications will be based on the APTS.

CCI [Redacted]

All disallowed medications entered in the eCRF, which will be identified via a clinical review of the coded medication data in the eCRF, will be listed based on the APRS. The listing will include the generic drug name, the duration, the start and end dates, and dosing information.

CCI [Redacted]

[Redacted]	[Redacted]	[Redacted]	[Redacted]
[Redacted]	[Redacted]	[Redacted]	[Redacted]
[Redacted]	[Redacted]	[Redacted]	[Redacted]
[Redacted]	[Redacted]	[Redacted]	[Redacted]
[Redacted]	[Redacted]	[Redacted]	[Redacted]
[Redacted]	[Redacted]	[Redacted]	[Redacted]
[Redacted]	[Redacted]	[Redacted]	[Redacted]
[Redacted]	[Redacted]	[Redacted]	[Redacted]

[Redacted]

10 Exposure

For the IMP Visit, information related to infusion completed as planned in full (yes/no), infusion temporarily interrupted (yes/no), and infusion lasted longer than 30 (+15) minutes (yes/no), as well as descriptive statistics for the duration of infusion (this duration includes duration of any infusion interruptions), and duration of temporary interruptions will be summarized by actual treatment group.

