UK-UKN-YYYY:

- If the year is equal to the year of treatment start date, the adverse event start date is imputed with treatment start date
- If the year is prior to the year of treatment start date, the adverse event start date is imputed with 31-DEC-YYYY
- If the year is after the year of treatment start date, the adverse event start date is imputed with 01-JAN-YYYY

If the adverse event start date is completely missing, it will be set equal to treatment start date.

End Dates

Missing adverse event end dates will not be imputed.

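### SAP 22.3.4 moves a year-only medication stop date to 31 December with no cap, so a drug already recorded as stopped at screening can be classed as concomitant

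*SAP*

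**What the plan says.** SAP section 22.3.4 has two rules for partial stop dates. With only the day unknown: "UK-MMM-YYYY: Medication end date is imputed with the last day of the month". With day and month unknown: "UK-UKN-YYYY: Medication end date is imputed with 31-DEC-YYYY". Neither refers to the Screening Visit or the infusion.

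For start dates it borrows another rule: "The algorithm for imputing the start dates will follow the one used for imputing adverse event start dates, see section 22.3.5". For a treated participant with a year-only start, section 22.3.5 says: "If the year is equal to the year of treatment start date, the adverse event start date is imputed with treatment start date". For no start date at all: "If the adverse event start date is completely missing, it will be set equal to treatment start date". Section 22.3.5 also moves an imputed start back to the end date if it would otherwise fall later.

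Section 22.3.4 gives the purpose of the imputation as assigning the section 9 categories. There a drug is prior only if it ended ahead of the infusion. The other category reads: "Concomitant medication: continued after IMP infusion or started at or after IMP infusion". Section 22.3.4 makes a drug marked as ongoing concomitant, but does not say that a drug recorded as no longer taken stays prior.

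Two further places bear on preventives. Protocol Appendix II bars them from one week before the Screening Visit. SAP section 22.1.3 says that once the preventive-therapy intercurrent event occurs, "the data collected after preventive medication intake will be disregarded and set to missing".

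**The concern.** Recent medication and failed preventives are both collected at the Screening Visit, at least 28 days before infusion. If the record made then shows that a drug had been stopped, the drug cannot have run past the infusion. The 31 December rule overrides that information whenever the month is unknown and the year is the infusion year.

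The SAP avoids this elsewhere. Section 22.3.3 classifies medical disorders by reported ongoing status and imputes no dates. Section 13.1.3 lets the investigator's causality assessment override the classification of an adverse event with an incomplete start date. Medications have no comparable safeguard.

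At stake is the accuracy of the prior and concomitant medication tables. Preventives matter most, because their use is an intercurrent event in the primary estimand and section 12.3.2 refers the reader to section 9 for its presentation. A false entry there would show a participant on a barred drug after infusion.

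**Working it through.** The plan gives no figure to reproduce here, so the check is to apply its rules to dated records.

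**Inputs.** Stop and start rules: SAP 22.3.4 and 22.3.5. Categories: SAP section 9. Screening to infusion, 28 to 30 days: SAP 4.2. One-week washout for preventives: Protocol Appendix II.

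**Worked records.** Take infusion on 29 June 2022 and screening 28 days earlier, on 1 June 2022. All stops below are truly before screening.

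| Recorded start | Recorded stop | Imputed start | Stop used | Section 9 class |
|---|---|---|---|---|
| year 2022 | year 2022 | 29 Jun 2022 | 31 Dec 2022 | concomitant (false) |
| missing | year 2022 | 29 Jun 2022 | 31 Dec 2022 | concomitant (false) |
| year 2021 | year 2022 | 31 Dec 2021 | 31 Dec 2022 | concomitant (false) |
| year 2021 | year 2021 | 31 Dec 2021 | 31 Dec 2021 | prior (true) |
| year 2022 | 15 Mar 2022 | 15 Mar 2022, pulled back | 15 Mar 2022 | prior (true) |
| year 2021 | Mar 2022 | 31 Dec 2021 | 31 Mar 2022 | prior (true) |

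In the first two rows the drug appears to start on the infusion day. The pull-back of the start date does not help, because the end date is itself imputed as 31 December.

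**All infusion dates in one year.** I applied the rules to 365 infusion dates, 3 screening lengths (28, 29 and 30 days) and each true stop from 7 to 90 days before screening (84 values): 365 × 3 × 84 = 91,980 combinations. The even spread of stops is an assumption made to exercise the rule.

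- Year-only stop: 72,450 of 91,980 (78.8%) came out as concomitant. These are exactly the combinations whose stop year equals the infusion year. The other 91,980 − 72,450 = 19,530 have an earlier stop year, and none was misclassed.
- Month-and-year stop: 0 of 91,980.
- Known stop date: 0 of 91,980, whatever the start date.

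With stops from 1 to 90 days before screening, so that the washout need not be met, there are 365 × 3 × 90 = 98,550 combinations. Year-only stops were misclassed in 78,435 (79.6%), again all the same-year ones, and month-and-year stops in 32 (0.03%).

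**Why the month rule is safe after washout.** The true stop is at least 7 + 28 = 35 days before infusion. Moving it to month end adds at most 30 days, so the imputed stop is still at least 35 − 30 = 5 days before infusion.

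The 78.8% is the share of same-year stops in this grid. It is not an estimate of how often the error would occur in the trial.

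**The case against.** The strongest reply is that the trigger is narrow and the consequence descriptive. Much of it stands.

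- **Frequency.** Protocol chapter 12 requires start and stop dates, or the treating physician's confirmation of the same information, as evidence of each failed preventive. Sites must also verify washouts, which is hard with the stop month unknown. A ten-year look-back does not enlarge the problem, since any stop year before the infusion year is classed correctly. A reader might multiply 230 participants by 2 to 4 failures, giving 460 to 920 records, and apply a guessed share to them. The documents do not support that. They give no rate of year-only dates; SAP section 8 summarises failed preventives separately; and a failure can be a contraindication, where the drug may never have been taken.
- **Primary endpoint.** A reader might infer that a false Day 0 start deletes all 28 primary diary days through section 22.1.3. The documents do not show this. Section 22.3.4 names only the section 9 categories as its purpose, 22.1.3 does not say which dates set the event, and 12.3.2 points to section 9 only for presentation. Parts of section 9, and section 21.2 on the estimand strategy for intercurrent events, are redacted and may hold a dating rule.
- **Start-date rule.** The borrowed adverse-event rule does no harm when the stop date is known.
- **Safeguards.** Disallowed medications are identified by clinical review of coded data for a listing, and section 17 provides for blinded data review. A barred drug apparently running from the infusion day to year end would probably be noticed. But no visible text says that such a review changes the section 9 category.

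What the reply does not remove is the rule itself: read literally, it misclasses every record that meets the trigger.

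**Conclusion.** The point holds in a limited form. Section 22.3.4 is wrong as written for one kind of record: a drug recorded at Visit 1 as already stopped, with a year-only stop in the infusion year. Every such record is classed as concomitant. The stop rule causes the error; the start rule only adds an apparent start on the infusion day when the start is year-only in that year or missing.

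The size is modest. The shown effect is false entries in the prior and concomitant medication tables, and possibly in the section 9 presentation of preventive use. An effect on the primary analysis is possible but not shown, and no direction of bias can be stated. The number of affected records cannot be estimated. The conclusion assumes that 22.3.4 is programmed as it reads and that no redacted text in section 9 or 21 overrides it.

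**What to change.** In section 22.3.4, state that a medication recorded at the Screening Visit as stopped stays in the prior category, with its imputed stop and start dates no later than the Screening Visit date. In the worked example the stop becomes the earlier of 31 December and 1 June 2022, that is 1 June. This is before the infusion on 29 June, so the drug is prior, and the existing pull-back moves the start to 1 June as well.

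For the preventive-therapy intercurrent event, state in section 22.1.3 that it is not set from an imputed date when the record shows that the drug stopped before screening. Settle other partial dates after infusion by blinded review before unblinding, for instance at the Classification Meeting in SAP section 5. Requiring a fully reported start after infusion would be too strict: it could miss a preventive truly started after infusion whose start day is unknown and which has since stopped.

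The cost is a few sentences in the SAP, a small programming change and some blinded review. No new data are needed.
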